8 ADVERSE EVENTS

See CORE SOP012_v02 for a description of all adverse events, including management and reporting.

Any observations taking place prior to determining that a subject meets all inclusion/ exclusion criteria for the study and which are not related to the performed study procedures are not considered an AE. An AE can be any unfavourable and unintended sign, symptom, or disease temporarily associated with a study procedure, whether there is a causal relationship or not.

9 DISCONTINUATION FROM THE STUDY

Participants may be discontinued at the discretion of the investigator in consideration of participant safety or protocol compliance, or at discretion of the participant. Participants discontinued from a study will be reimbursed \$20 per hour for their active involvement in the study (including the initial screening visit). Upon discontinuing, a participant will be offered the option of their data being withdrawn from future statistical analysis. The following is a list of possible reasons for discontinuation from the study:

- Screening failure: Participants will be discontinued if they do not meet the inclusion and exclusion criteria outlined in section 5.2.3.
- Unacceptable performance with products to be used in study: Participants may be discontinued if they are unable to achieve acceptable comfort and /or vision with the study products.
- Positive slit lamp finding: Participants may be permanently discontinued from the study depending on the severity of the condition and on the judgement of the investigator.
- Adverse event: If a participant experiences an adverse event during the study they may be discontinued based on the clinical judgement of the investigator.
- Symptoms: If the participant has persistent symptoms they may be discontinued based on the clinical judgement of the investigator.
- Disinterest, relocation or illness: The participant may choose to discontinue due to reasons within or beyond their control.
- Violation of protocol or non-compliance: The participant will be discontinued if they are unable or unwilling to follow the protocol specified visit schedules and/or study procedures.
- Instillation of topical ocular medication: The participant may be discontinued if they elect to use a topical ocular medication during the study unless that topical ocular medication is prescribed for a limited duration (less than two weeks) to treat a transient condition; in this case the participant may remain an active participant (at the discretion of the investigator) after stopping topical ocular medication following resolution of the ocular condition).
- Lost to follow-up: The participant will be discontinued if they cannot be contacted and do not return for a final exit visit, and if the investigator has made a reasonable effort to contact the participant for a final study visit.

- Premature termination of the study by CORE or the Office of Research Ethics at the University of Waterloo.

A discontinuation form (ADMIN 3), stating the reason for discontinuation will be completed, which requires the signatures of both the participant and the investigator except where the participant is lost to follow-up in which case only the signature of the investigator is required.

All discontinuations including their reasons will be included in the final report.

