5.2 STUDY POPULATION

5.2.1 SAMPLE SIZE CALCULATION

The sample size required for a 2-tailed matched paired t-test to detect a difference of at least 5 points in subjective ratings, with $\alpha=0.05$, power = 0.95, and $\text{diff}/\text{SD} = 0.60$ is 39 (Figure 1).

Therefore, a sample size of 43 is being proposed to account for possible dropouts and screen failures (for which not all visits are required).

[figure not shown]

Figure 1: Sample size calculation

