5.2.2 NUMBER OF PARTICIPANTS

Up to 60 participants may be screened using CORE records and advertising approved by the UW Office of Research Ethics. Approximately 43 participants will be dispensed / randomized with study products, with a target of number of 39 participants completing the study. Informed consent will be obtained for all participants prior to their enrolment in the study (Appendix 1).

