6 MONITORING PROTOCOL ADHERENCE

All personnel involved in this study will be listed on a delegation log and their training will be documented. Consent documentation will be reviewed by personnel not involved in the consent process. Visit windows will be reviewed when determining the analysis cohort. All adverse events and protocol deviations will be reviewed by the Lead Investigator. Serious adverse events and major protocol deviations will be reviewed by the Principal Investigator.

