11 STATISTICAL ANALYSIS AND DATA MANAGEMENT

11.1 STATISTICAL ANALYSIS

All data will be analyzed by CORE at the University of Waterloo. Descriptive statistics will be provided on information regarding baseline variables (e.g. age, gender). Differences between lenses and differences over time will be compared using either Paired t-tests or Wilcoxon matched pairs, or using ANOVA, as applicable; statistical significance will be set at 5%. The appropriate tests will be selected based on tests of normality - non-parametric tests will be used for data not showing a normal distribution. For assessments conducted for each eye separately, the right eye will be used for analysis.

The following statistical tests will be performed for the listed comparisons after 1 month of DT1 wear vs habitual DD CL wear (Table 4).

Table 4: Statistical procedures

Comparison	Statistical test
CLDEQ-8 ratings between lenses (habitual DD vs. DT1)	2-sided paired t-test
Subjective ratings between lenses (habitual DD vs. DT1)	2-sided paired t-test

Subjective ratings over time (from home ratings) for DT1	Repeated Measures ANOVA
Comparisons as above, but on groups stratified by DED subtype (evaporative/aqueous deficient/mixed disease)	2-sided paired t-test

In addition, equivalence and superiority for the test lens (DT1) vs the habitual lens will be evaluated for the primary outcome variables, with a change in subjective ratings of 5 points and a difference of 0.5 hours in average and comfortable wear time being considered as a clinically relevant difference.

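### If participants stop DT1 for poor comfort or persistent symptoms, no exit rating is scheduled and the 1-month paired comparison omits them, which would favour DT1

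*Combined protocol and SAP*

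**What the plan says.** All references are to the combined protocol and SAP.

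- **Endpoints (section 2).** End-of-day comfort and dryness on a 0 to 100 scale, average wear time and comfortable wear time are primary.
- **Discontinuation (section 9).** "Participants may be discontinued if they are unable to achieve acceptable comfort and /or vision with the study products". Persistent symptoms are a separate listed reason, at the investigator's judgement. On discontinuing, "a participant will be offered the option of their data being withdrawn from future statistical analysis". A form giving the reason is completed, and all discontinuations with reasons go into the final report.
- **Comparison (section 11.1).** The tests in Table 4 are for comparisons "after 1 month of DT1 wear vs habitual DD CL wear". Subjective ratings and CLDEQ-8 are compared by 2-sided paired t-test, with a Wilcoxon alternative if the data are not normal. The relevant difference is 5 points for ratings and 0.5 hours for wear times.
- **Timing of DT1 ratings (sections 5.4.2, 5.5.2 and Table 3).** The in-office DT1 rating is at Visit 3, 29 to 34 days after dispensing. Home ratings on DT1 are due on Days 1, 3, 5, 7, 21 and 28.
- **Numbers (sections 5.2.1 and 5.2.2).** About 43 are to be dispensed, "with a target of number of 39 participants completing the study".
- **Cohort (section 6).** The only statement on who is analysed is "Visit windows will be reviewed when determining the analysis cohort".

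**The concern.** A participant who gives up DT1 because it is uncomfortable is lost because of a poor value of the primary endpoint. A paired test uses only complete pairs. Without a 1-month DT1 value, and without a rule that supplies another, that participant's pair is absent.

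The loss acts in one direction. Habitual-lens data are collected before DT1 is dispensed, so poor comfort on DT1 can only remove pairs that are unfavourable to DT1. The study is not randomized, so no concurrent arm has similar losses to offset this. Participants must be symptomatic to enrol (section 5.2.3), so stopping for discomfort is a realistic event, and the plan itself expects some dispensed participants not to complete.

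At stake is a claim that DT1 is more comfortable or worn longer, resting on a sample from which some of those it failed have been removed.

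**Working it through.** **1. Inputs.** From section 5.2.1: 2-sided paired t-test, difference 5 points, alpha 0.05, power 0.95, difference/SD 0.60. Derived: SD of the paired difference = 5/0.60 = 8.33 points. From section 5.2.2: 43 dispensed, 39 completing, so 4 losses, 4/43 = 9.3%. The rate of comfort stops and the ratings of those who stop are not given; both are assumed below.

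**2. The plan's own figure.** Noncentral-t power with n − 1 degrees of freedom and noncentrality 0.60 × √n first reaches 0.95 at n = 39 (power 0.9546). The stated 39 is reproduced. At n = 43 the power is 0.970.

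**3. Shift in the mean.** If k of 43 are missing and their mean change is *gap* points worse than that of completers, the completer mean exceeds the all-dispensed mean by (k/43) × gap.

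| k | gap 5 | gap 10 | gap 15 | gap 20 |
|---|---|---|---|---|
| 2 | 0.23 | 0.47 | 0.70 | 0.93 |
| 4 | 0.47 | 0.93 | 1.40 | 1.86 |
| 8 | 0.93 | 1.86 | 2.79 | 3.72 |

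With 4 losses, a 5-point bias would need a gap of 5 × 43/4 = 53.75 points.

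**4. False-positive rate with no true difference.** Paired differences were simulated as normal with mean 0 and SD 8.33 for 43 participants (200,000 repetitions), and the lowest k were removed.

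| lowest k removed | shift (points) | chance of a significant result favouring DT1 |
|---|---|---|
| 0 | 0 | 2.5% |
| 1 | +0.44 | 6.1% |
| 2 | +0.81 | 11.2% |
| 4 | +1.48 | 26.4% |

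Removing exactly the worst k is the sharpest form of selection. With a dropout probability that rises gradually as the difference worsens (logistic, mean 9.3%), the shift is about +0.4 to +1.1 points.

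**5. Effect on a positive result.** Let 39 completers have mean +5 and SD 8.33. SE = 8.33/√39 = 1.334, t = 5/1.334 = 3.75, p = 0.0006, 95% CI 2.3 to 7.7. Now add 4 discontinued participants, all at value v:

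- mean = (39 × 5 + 4v)/43
- sum of squares = 38 × 8.33² + (39 × 4/43) × (5 − v)², with 42 degrees of freedom

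For v = −20: mean = (195 − 80)/43 = 2.67; sum of squares = 2638.9 + 3.628 × 625 = 4906; SD = √(4906/42) = 10.81; SE = 10.81/√43 = 1.65; t = 1.62.

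| v | mean | p | lower 95% limit |
|---|---|---|---|
| −10 | 3.6 | 0.013 | +0.8 |
| −15 | 3.1 | 0.043 | above 0, since p < 0.05 |
| −20 | 2.7 | 0.11 | −0.65 (upper 6.0) |
| −30 | 1.7 | 0.38 | −2.25 |

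With fewer added at −20, two give p = 0.018 and three give p = 0.0504.

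**The case against.** Several points on the other side are sound.

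- **It is conditional.** Discontinuation for comfort is permitted, not required, and the same bullet covers vision. DT1 is first fitted at Visit 1, so some such stops would come before dispensing and lose no pair. Many listed reasons are unrelated to comfort, and section 5.2.1 says the allowance of 4 also covers screen failures.
- **The plan is silent rather than explicit.** A reader might infer that it prescribes a completers analysis. No section defines one: 39 is a completion target, and section 6 does not say that discontinued participants are excluded. A reader might also infer that visit windows are judged once results are known, but section 6 gives no timing.
- **The source of the 1-month rating is not fully fixed.** Table 4 does not say whether the between-lens rating is the in-office one or the Day 28 home one. Someone who stops before Day 28 has neither, so the gap remains.
- **Early DT1 data may exist.** Home ratings start on Day 1, but the plan gives them no role in the between-lens test when the 1-month value is missing. They describe a single day, whereas the in-office form asks about a typical day over the previous month (section 5.5.2), so carrying one forward as the primary value would be debatable.
- **The scenarios in step 5 are severe.** A value of −20 lies 25/8.33 = 3.0 SD below the completer mean, and −30 lies 4.2 SD below. Four at −10 or −15 leave the result significant.
- **Reasons for discontinuation will be reported.** This lets a reader see comfort stops, but it does not bring those participants into the test.

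These points limit the certainty and size of the problem. They do not remove the mechanism or its direction.

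**Conclusion.** The concern holds in conditional form. If participants stop DT1 after dispensing because of poor comfort or persistent symptoms, the plan collects no DT1 rating from them at exit and the 1-month paired comparison has no value for them. The comparison of comfort, dryness and wear time would then be biased towards DT1.

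The probable shift in ratings at the planned loss is a fraction of the 5-point margin. A significance claim is more fragile, as the roughly tenfold rise in the one-directional error rate under worst-case selection shows. These sizes rest on an SD derived from the planning values, normally distributed differences, all 4 losses being comfort or symptom stops, and assumed gaps.

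A reader might infer that four poor outcomes would reverse the finding. The figures do not show that: with four at −20, significance is lost but the mean still favours DT1, and the lower limit stays above −5 in every scenario tried. A conclusion that DT1 is not worse by 5 points would survive; a conclusion that it is better might not.

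**What to change.** 1. **Section 9:** have every participant who discontinues after dispensing complete the existing 0 to 100 rating form, wear times and CLDEQ-8 for DT1 at exit. The rules on when someone is discontinued need no change for this.
2. **Section 11.1:** define the primary population as all participants dispensed DT1 who have a habitual rating. Use the Visit 3 value or, for those who discontinued, the exit rating.
3. **Where neither exists:** use the DT1 home ratings in a sensitivity analysis, for example a mixed model, or assign an unfavourable value to comfort or symptom stops. Do not carry a single-day rating forward as the primary value.
4. **Reporting:** show the completers analysis as supportive. Beside the estimate, give the number who stopped for comfort or symptoms and the number whose data were withdrawn at their request, since no analysis can recover the latter.

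The cost is one existing form at exit and a few lines in section 11.1. No extra participants are needed, since the calculated power at n = 43 is above the planned 0.95. The drawback is that a few exit ratings will reflect less than a month of wear, and for very early stops less than the two-week period that CLDEQ-8 asks about.

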10 STUDY COMPLETION AND REMUNERATION

At the last scheduled protocol visit a study completion form (ADMIN 2) will be completed, which requires the signatures of both the participant and the investigator.

Once their involvement in the study is complete, participants will be informed about receiving feedback following study completion in the Letter of Appreciation (ADMIN 1).

Participant remuneration will be \$90 for completing the study this includes \$70 for active time and \$20 for completing the at-home questionnaires.

11 STATISTICAL ANALYSIS AND DATA MANAGEMENT

11.1 STATISTICAL ANALYSIS

All data will be analyzed by CORE at the University of Waterloo. Descriptive statistics will be provided on information regarding baseline variables (e.g. age, gender). Differences between lenses and differences over time will be compared using either Paired t-tests or Wilcoxon matched pairs, or using ANOVA, as applicable; statistical significance will be set at 5%. The appropriate tests will be selected based on tests of normality - non-parametric tests will be used for data not showing a normal distribution. For assessments conducted for each eye separately, the right eye will be used for analysis.

The following statistical tests will be performed for the listed comparisons after 1 month of DT1 wear vs habitual DD CL wear (Table 4).

Table 4: Statistical procedures

Comparison	Statistical test
CLDEQ-8 ratings between lenses (habitual DD vs. DT1)	2-sided paired t-test
Subjective ratings between lenses (habitual DD vs. DT1)	2-sided paired t-test

Subjective ratings over time (from home ratings) for DT1	Repeated Measures ANOVA
Comparisons as above, but on groups stratified by DED subtype (evaporative/aqueous deficient/mixed disease)	2-sided paired t-test

In addition, equivalence and superiority for the test lens (DT1) vs the habitual lens will be evaluated for the primary outcome variables, with a change in subjective ratings of 5 points and a difference of 0.5 hours in average and comfortable wear time being considered as a clinically relevant difference.

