5.2.3 INCLUSION AND EXCLUSION CRITERIA

A person is eligible for inclusion in the study if he/she:

1. Is at least 17 years of age and has full legal capacity to volunteer;
2. Has read and signed an information consent letter;
3. Is willing and able to follow instructions and maintain the appointment schedule;
4. As per TFOS DEWS II², have dry eye symptoms (without CL wear) as determined by an OSDI score of ≥ 13 and at least **one** of the following:
 - a. Tear osmolarity $\geq 308\text{mOsm/L}$ or interocular difference $>8\text{ mOsm/L}$
 - b. Non-invasive tear breakup time of < 10 seconds in at least one eye
 - c. More than 5 spots of corneal staining OR > 9 conjunctival spots in at least one eye
5. Reports dryness while wearing DD CLs with CLDEQ-8 score ≥ 12 and $\leq 20^3$
6. Habitually wears soft spherical DD CLs with a power between +6.00D and -10.00D
7. Manifest spectacle cyl $\leq 1.00\text{DC}$ in either eye
8. BCVA $\leq 0.20\text{ log MAR}$ each eye with habitual & DT1
9. Acceptable fit with habitual & DT1
10. Willing to wear DT1 CLs at least 3 days per week and 6 hours per day throughout the study

A person will be excluded from the study if he/she:

1. Is participating in any concurrent clinical or research study;
2. Has any known active* ocular disease and/or infection;
3. Has a systemic condition that in the opinion of the investigator may affect a study outcome variable;
4. Is using any systemic or topical medications that in the opinion of the investigator may affect a study outcome variable;
5. Has known sensitivity to the diagnostic pharmaceuticals to be used in the study;
6. Is pregnant, lactating or planning a pregnancy at the time of enrolment (by self-report);

7. Is aphakic;
8. Has undergone refractive error surgery;
9. Has taken part in another clinical research study within the last 14 days;
10. Current habitual wearer of DT1
11. Any ocular and/or systemic conditions or concomitant medication to contraindicate contact lens wear or be expected to interfere with the primary outcome variables.

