5.5.6 NON-INVASIVE BREAK-UP TIME

The participant will be seated in front of a device (OCULUS Keratograph (K5M) that will project rings of light (Placido discs) onto the tear film. The participant will be asked to keep their eyes open for as long as they can and the time until the rings first begin to distort or break will be recorded. Three measurements will be taken for each eye to obtain an average value.

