5.5.7 TEAR MENISCUS HEIGHT

The participant will be seated in front of the OCULUS Keratograph (K5M) with their chin on the chin rest and head against the forehead rest. The investigator will select the Tear meniscus height feature and will take images of the ocular surface of each eye.

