5.5.8 TEAR OSMOMETRY

The participant will be asked to lean their head back and gaze towards the ceiling. The TearLab™ pens are loaded with sterile test cards. The pen will be used to gather ~50nL of tears

from one eye at a time, from the lower lateral tear meniscus without making direct contact with the eye. The pen will be docked to the base instrument to determine tear osmolarity.

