5.5.11 MEIBOMIAN GLAND EXPRESSIBILITY

Meibomian gland dysfunction results in stagnation of the meibum (oil) within the glands. The ease of expression of the gland and the quality of the expressed contents therefore provides an indication of the functional capabilities of the glands. The MG Evaluator (TearScience/J&J) will be used to apply a pressure of 1.2g/mm^2 to the lower eyelid just inferior to the lid margin in three areas – nasal, central and temporal. Five consecutive glands in each area will be assessed for expressibility. Glands will be graded as follows: 0: blocked, 1: inspissated (toothpaste), 2: cloudy with debris, 3: clear, the results for each location will be summed (Meibomian gland score).

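### The right-eye-only rule in 11.1 does not fit Visit 1 signs that 5.2.3 accepts in either eye or as a between-eye difference, and it leaves collected left-eye data out of lens comparisons of per-eye clinical signs

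*Combined protocol and SAP*

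**What the plan says.** Section 11.1 sets one rule for all per-eye data: "For assessments conducted for each eye separately, the right eye will be used for analysis". It names no exception.

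Section 5.2.3 requires an OSDI score of at least 13 plus at least one of three signs:

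- Osmolarity: a level of 308 mOsm/L or more (no eye named), "or interocular difference" above 8 mOsm/L.
- Break-up time: "Non-invasive tear breakup time of < 10 seconds in at least one eye".
- Staining: "More than 5 spots of corneal staining OR > 9 conjunctival spots in at least one eye".

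The procedures collect data from both eyes for most of these tests. For break-up time, "Three measurements will be taken for each eye to obtain an average value" (5.5.6). For meniscus height, the investigator "will take images of the ocular surface of each eye" (5.5.7). Tears for osmometry are taken "from one eye at a time, from the lower lateral tear meniscus" (5.5.8). Both eyes are stained (5.5.10), and acuity is recorded right, left and binocular at Visits 2 and 3 (5.4.2). The meibomian gland test applies pressure "to the lower eyelid just inferior to the lid margin in three areas" (5.5.11) without saying which eye.

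Section 5.4.2 uses the Visit 1 tests both for eligibility and to assign the DED subtype. Subtype classification is the first objective (section 2) and a stratifier in Table 4. No section says which eye, or what combination of eyes, determines it. Section 5.1.1 says clinical signs will be compared between the habitual lens and DT1, although Table 4 lists no such comparison.

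**The concern.** Two separate things follow from applying one eye rule to everything.

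First, the cohort is defined by findings in either eye or by a difference between eyes, while the analysis section looks at one eye. Taken literally, the baseline description would omit one entry criterion and could show some participants without the sign that admitted them. This touches the first objective, which is to describe and classify DED. It also leaves the eye basis of the subtype open, to be settled by the analyst later.

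Second, left-eye measurements made at every visit would not contribute to the comparison of clinical signs between lenses. What is lost there is precision, not validity.

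**Working it through.** **1. The plan's own figure.** Section 5.2.1 gives 39 completers for a two-sided paired t-test with alpha 0.05, power 0.95 and diff/SD 0.60 (5 points, so an implied SD of 5/0.60 = 8.33). Exact power from the noncentral t distribution is 0.955 at n = 39 and 0.9496 at n = 38, so 39 is reproduced. It is set on 0–100 ratings given once per participant, so no eye rule enters and N does not change.

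**2. Which outcomes the rule reaches.**

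- Not reached: comfort and dryness ratings, both wear times, CLDEQ-8 and binocular acuity. No by-eye version of these is described.
- Reached: the Visit 1 signs measured by eye, staining, monocular acuity, and hyperemia, lens fit, wettability and deposits where these are recorded by eye. Sections 5.5.9 and 5.5.10 do not state by-eye recording for those last four.

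**3. Visit 1 signs, 5.2.3 against 11.1.**

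| Criterion in 5.2.3 | Right eye only |
|---|---|
| Osmolarity, between-eye difference > 8 mOsm/L | Cannot be computed |
| Osmolarity, level ≥ 308 mOsm/L | Computable for the right eye; 5.2.3 names no eye |
| Break-up time < 10 s in either eye | Left-eye qualifier appears negative |
| Staining count in either eye | Left-eye qualifier appears negative |

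The first row follows from the definition and needs no assumption. The number of left-eye qualifiers cannot be derived from the documents. As illustration only, suppose the eyes are affected equally often and a share c of those positive on a sign are positive in both eyes. Then (1 − c)/2 are positive in the left eye only: 5% at c = 0.9, 15% at c = 0.7 and 25% at c = 0.5. This is per sign, and a participant may qualify on several signs. It is not a count of wrong subtypes.

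**4. Precision of lens comparisons of per-eye signs.** Let the DT1-minus-habitual change have the same variance in each eye, with between-eye correlation ρ. The documents give no ρ, so it is assumed.

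- Variance of the two-eye mean ÷ one-eye variance = (1 + ρ)/2.
- Reduction in SE = 1 − √((1 + ρ)/2).
- Right-eye-only participants giving the same information = 39 ÷ ((1 + ρ)/2).
- 95% CI half-width with one eye = t(0.975, 38 df)/√39 = 0.324 one-eye SDs. Multiply by √((1 + ρ)/2) for the two-eye mean.

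| ρ (assumed) | Variance ratio | SE reduction | Equivalent n | CI half-width (one-eye SDs) |
|---|---|---|---|---|
| 0.5 | 0.75 | 13.4% | 52.0 | 0.281 |
| 0.8 | 0.90 | 5.1% | 43.3 | 0.308 |
| 0.9 | 0.95 | 2.5% | 41.1 | 0.316 |
| 0.95 | 0.975 | 1.3% | 40.0 | 0.320 |

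**The case against.** The strongest reply is that a prespecified single-eye rule is a sound way to avoid treating two eyes of one person as independent. That stands: the right-eye comparison carries no bias or error-rate problem. The precision gain also rests on an assumed correlation, is negligible if the eyes move almost together, and concerns outcomes with no stated hypothesis or power target. For 0–4 grades 11.1 may select the Wilcoxon test, to which the SE figures do not apply exactly.

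It can also be said that the right-eye sentence closes a paragraph mainly about lens differences and changes over time, so it was never meant for screening. Eligibility is decided under 5.2.3 and confirmed in the participant record (14.6). That part stands too: eligibility works as written. But the same paragraph also covers descriptive statistics for baseline variables, and the sentence has no limit, so the narrower reading is not secured by the text.

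A reader might go further and infer that the subtype strata in Table 4 are misclassified. The documents do not support this. Section 5.4.2 assigns the subtype to the participant at Visit 1 using a cited guideline, and nothing says that the right-eye rule feeds that assignment. The eye basis is unstated, which is a gap rather than an error shown. Nor should this review fill the gap with a diagnostic rule: counting a test as positive if either eye is positive could, for example, label as mixed a participant with an evaporative sign in one eye and an aqueous-deficient sign in the other.

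**Conclusion.** The concern holds in limited form. The unrestricted right-eye rule does not fit the Visit 1 signs: it cannot express the between-eye osmolarity criterion at all, and it can present left-eye qualifiers as negative, in a number the documents do not allow anyone to calculate. For per-eye clinical signs compared between lenses, the right-eye analysis is valid but less precise than the data permit. The size of that loss depends wholly on the assumed correlation and on equal variances in the two eyes; it ranges from modest at 0.5 to negligible at 0.95.

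It would be wrong to infer that the main lens comparison loses data or power. The primary endpoints, CLDEQ-8, the overall Table 4 comparisons and the sample size do not depend on the rule. This is a cheap improvement, not a threat to the trial's main conclusions.

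**What to change.** 1. **Visit 1 signs.** State in 11.1 that the right-eye rule does not govern the eligibility signs. Summarise break-up time and staining on the either-eye basis of 5.2.3, and report the between-eye osmolarity difference as its own variable. Because 5.5.10 grades staining on the Efron scale while 5.2.3 uses spot counts, the staining summary should report whether the 5.2.3 criterion was met in either eye.
2. **DED subtype.** Reconcile 11.1 with 5.2.3 and 5.4.2 by stating the eye basis of the subtype before the data are analysed. The choice of diagnostic rule is for the investigators.
3. **Habitual versus DT1.** For outcomes recorded in both eyes (staining, monocular acuity, and hyperemia or lens performance where recorded by eye), analyse the participant mean of both eyes with the paired test that 11.1 would select, t or Wilcoxon. This keeps one value per participant. Keep the right-eye result as a sensitivity analysis.

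The cost is SAP wording and slightly more analysis work. No visits, participants or measurements are added, because the two-eye mean is used only where both eyes are already recorded.
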